10.1.4 Summary of the Risks and Benefits

Blood draws: The risks of drawing blood include bleeding at the puncture site, bruising and pain. These occur in a very small portion of the population.

Eliquis (apixaban): Direct oral anticoagulants, the class to which apixaban belongs to, have been shown to reduce the risk of stroke and systemic embolism in patients with non-valvular atrial fibrillation (NVAF). These agents are recommended over warfarin in eligible patients with NVAF and a CHA2DS2-VASc score ≥ 2 in men or ≥ 3 in women to reduce the risk of stroke and systemic embolism (1, LOE A). The risks for apixaban use in LVAD patients in this study are not known, particularly the risks associated with device thrombosis or stroke, but the risks are expected to be similar as use of apixaban for the prevention of stroke and systemic embolism in patients with NVAF. The most common (>1%) adverse reactions are related to bleeding as apixaban may cause serious, potentially fatal, bleeding. Compared with warfarin, DOACs reduce the risk of intracranial hemorrhage. Apixaban is not known to be teratogenic however it should not be used in pregnancy due to the increased risk of bleeding.

Coumadin (warfarin): Warfarin was the comparator to all DOACs in studies evaluating DOAC use for patients with NVAF. Warfarin is standard anticoagulation for LVAD patients. Warfarin is recommended in patients with atrial fibrillation and a CHA2DS2-VASc score ≥ 2 in men or ≥ 3 in women to reduce the risk of stroke and systemic

embolism who are not considered eligible for a DOAC (moderate-to-severe mitral stenosis or a mechanical heart valve) (1, LOE A). The most common (>1%) adverse reactions are related to bleeding as warfarin may cause serious, potentially fatal, bleeding. Warfarin is associated with a higher risk of intracranial and gastrointestinal bleeding when compared with apixaban in NVAF and VTE. Warfarin is known to be teratogenic and should be avoided in the first trimester of pregnancy.

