11.2 Follow-up Evaluations

Study Visit 1 (2 weeks post-randomization +/- 7 days) – Virtual Visit

At this visit, two weeks after randomization, interim history, review of medications, adherence and tolerance assessment, and adverse event monitoring.

Study Visit 2 (4 weeks post-randomization +/- 7 days)

At this visit, four weeks after randomization, interim history, review of medications, physical examination, laboratory testing (white blood cells, hemoglobin, platelet count, sodium, potassium, BUN, creatinine, magnesium, AST/ALT, total and direct bilirubin, albumin, total protein, alkaline phosphatase, activated partial thromboplastin time, prothrombin time/INR, LDH, fibrinogen, d-dimer and Anti-Xa level), adherence and tolerance assessment, and adverse event monitoring. A biobank blood collection will be performed. Verification of listing status for transplant to ensure ongoing eligibility for study participation.

Study Visit 3 (6 weeks post-randomization +/- 7 days) – Virtual Visit

At this visit, six weeks after randomization, interim history, review of medications, adherence and tolerance assessment, and adverse event monitoring.

Study Visit 4 (8 weeks post-randomization +/- 7 days) – Virtual Visit with Labs

At this visit, eight weeks after randomization, interim history, review of medications, adherence and tolerance assessment, and adverse event monitoring. Remote lab testing will include white blood cells, hemoglobin, platelet count, sodium, potassium, BUN, creatinine, magnesium, AST/ALT, total and direct bilirubin, albumin, total protein, alkaline phosphatase, prothrombin time/INR, LDH.

Study Visit 5 (12 weeks post-randomization +/- 14 days)

At this visit, 12 weeks after randomization, interim history, review of medications, physical examination, laboratory testing (white blood cells, hemoglobin, platelet count, sodium, potassium, BUN, creatinine, magnesium, AST/ALT, total and direct bilirubin, albumin, total protein, alkaline phosphatase, activated partial thromboplastin time, prothrombin time/INR, LDH, fibrinogen, d-dimer and Anti-Xa level), adherence and tolerance assessment, and adverse event monitoring. A biobank blood collection will be performed. Verification of listing status for transplant to ensure ongoing eligibility for study participation.

Study Visit 6 (18 weeks post-randomization +/- 14 days) – Virtual Visit

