12 OUTCOME DETERMINATIONS

12.1 Primary Endpoint

Freedom from death or hemocompatibility related adverse events (stroke, device thrombosis, bleeding, aortic root thrombus and arterial non-CNS thromboembolism) at 24-weeks.

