12.2 Secondary Endpoints

- 1. Survival free of any stroke
- 2. Survival free of ischemic stroke
- 3. Survival free of hemorrhagic stroke
- 4. Survival free of device thrombosis
- 5. Survival free of aortic root thrombus
- 6. Survival free of gastrointestinal bleeding
- 7. Survival free of major non-gastrointestinal bleeding
- 8. All-cause mortality
- 9. Cardiovascular mortality

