17.2 Study Termination

The study may be terminated by the Sponsor at any time with suitable written notice to the reviewing IRB and applicable regulatory agencies. The study may be terminated by the DSMB based on concerns for significant harm to study participants based on criteria outlined in the DSMB charter. The following clinical events in the apixaban arm will result in an immediate pause of study enrollment for an evaluation by the independent DSMB:

- ≥ 2 thromboembolic events (ischemic stroke, arterial non-CNS embolism, device thrombosis, aortic root thrombus)
- ≥ 4 major bleeding events (Types 3-5)
- ≥ 2 deaths due to either thromboembolic events or major bleeding events

Patients who are already enrolled in the study will continue study-related activities during the enrollment pause.

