- **Aortic root thrombus:** thrombus located on the aortic valve or in the aortic cusp or aortic root which is visualized on echocardiography or CT imaging.

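### Aortic root thrombus counts only when imaging shows it, but no imaging is scheduled or logged, so a difference in how often the arms are imaged could not be told from a difference in thrombus

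*Combined protocol and SAP*

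**What the plan says.** Appendix B (section 19.2) defines aortic root thrombus as "thrombus located on the aortic valve or in the aortic cusp or aortic root which is visualized on echocardiography or CT imaging". The definition has no clinical, operative or autopsy route.

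The event is used in three places:

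- Section 12.1, the primary endpoint: "Freedom from death or hemocompatibility related adverse events (stroke, device thrombosis, bleeding, aortic root thrombus and arterial non-CNS thromboembolism) at 24-weeks".
- Section 12.2, secondary endpoint 5: "Survival free of aortic root thrombus".
- Section 17.2, the pause rule: "The following clinical events in the apixaban arm will result in an immediate pause of study enrollment", the first trigger being "≥ 2 thromboembolic events (ischemic stroke, arterial non-CNS embolism, device thrombosis, aortic root thrombus".

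The visit content contains no imaging. The week 12 entry in section 11.2 is typical: "At this visit, 12 weeks after randomization, interim history, review of medications, physical examination, laboratory testing", followed by adherence, adverse events, biobank sampling and transplant listing status. The baseline visit (11.1), the other follow-up visits (11.2), the phone and video contacts (11.3) and the Appendix C table likewise list no echocardiogram or CT.

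Treatment is open label (sections 7.2 and 9.1). Section 10.1.4 says: "The risks for apixaban use in LVAD patients in this study are not known, particularly the risks associated with device thrombosis or stroke". The same sentence goes on to say that risks are expected to resemble those of apixaban in non-valvular atrial fibrillation.

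**The concern.** An event that exists only on an image is counted as often as someone looks and it is there. The plan fixes neither the looking nor a record of it. Whatever imaging takes place is arranged outside the protocol, by clinicians who know the treatment.

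If one arm is imaged more, it will show more aortic root thrombus at the same true risk. More imaging on apixaban would make the drug look worse; less would hide harm. Neither intention-to-treat analysis nor the Cox model in section 15.3 can correct for this, because the imaging rate is not a recorded variable. Section 15.2 says the data will inform phase III design, so a component rate that partly reflects imaging habits would carry forward into that design.

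**Working it through.** **1. Is this component different from its neighbours?** Under Appendix B, suspected device thrombosis needs a clinical or device sign plus an accompanying event or intervention. Confirmed device thrombosis is framed as a major device malfunction. Arterial non-CNS thromboembolism needs an acute perfusion deficit. Aortic root thrombus needs only a positive image. Among the thrombotic components, it is the one that can be counted in a patient with no clinical sign.

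**2. Is imaging scheduled or recorded?** Sections 11.1 to 11.3 and Appendix C schedule none. Unplanned hospital, emergency and clinic evaluations go on an eCRF page (section 14.1.6 and Appendix B), but no imaging record is asked for. Section 14.1.7 keeps non-serious adverse events off the safety page unless antithrombotic dosing changes, so it is unclear how a silent thrombus reaches the database. The thromboembolic list in section 14.1.8 omits aortic root thrombus while that in section 17.2 includes it; the two should be reconciled.

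**3. Is there a plan figure to reproduce?** No. Section 15.2 states that the 40 patients were not statistically derived, and no event rate or imaging rate is given. What follows is illustration.

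**4. Inputs.** From the documents: 20 apixaban patients (sections 7.3 and 14.1.8), about 20 on warfarin (40 patients, 1:1), and a pause at 2 events, apixaban arm only (17.2). Assumed: true 24-week risk *p* of 5%, 10% or 15%, equal in both arms; share of cases imaged, and so counted, *d* = 80% on apixaban and 40% on warfarin.

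**5. Expected detected cases per arm = 20 × p × d.**

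| True risk | Apixaban, 80% | Warfarin, 40% | Excess per 20 | As share of 20 |
|---|---|---|---|---|
| 5% | 0.8 | 0.4 | 0.4 | 2% |
| 10% | 1.6 | 0.8 | 0.8 | 4% |
| 15% | 2.4 | 1.2 | 1.2 | 6% |

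The excess is 20 × p × (0.80 − 0.40). It adds to the composite only for patients with no other primary event. It also assumes that imaging does not depend on symptoms. If symptomatic thrombi are imaged in both arms, the excess is multiplied by the silent share, so these values are upper ends for the stated inputs.

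With a wider gap of 75% v 25% at 10% risk, the detected risks are 7.5% and 2.5%. The apparent hazard ratio for this component is ln(1 − 0.075)/ln(1 − 0.025), about 3.1, with no drug effect. Reversing the imaging shares reverses the sign.

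**6. Pause rule.** The chance that this component alone reaches the threshold is P(X ≥ 2), X ~ Binomial(20, p × d), with *d* the apixaban imaging share only.

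| True risk | d = 40% | d = 80% | d = 100% |
|---|---|---|---|
| 5% | 6% | 19% | 26% |
| 10% | 19% | 48% | 61% |
| 15% | 34% | 71% | 82% |

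For example, at 10% and 80%: p × d = 0.08 and 1 − 0.92^20 − 20 × 0.08 × 0.92^19 = 1 − 0.189 − 0.328 = 0.48.

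**The case against.** **Unequal imaging is assumed, not shown.** This stands. The trial has one center, and routine echocardiography on the same schedule in both arms is equally compatible with the text. A reader might infer from section 10.1.4 that apixaban patients will be imaged more. That sentence names device thrombosis and stroke, not aortic root thrombus, and ends by expecting similar risks, so it establishes neither unequal imaging nor a direction. Equally, the documents never mention routine imaging, so it cannot be relied on to equalize detection.

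**The composite is not captive to this component.** This also stands. A reader might conclude that the composite difference cannot be separated from surveillance. That goes too far: there are six components, bleeding is unrestricted in section 12.1, and secondary endpoint 5 lets this component be examined apart. That endpoint is itself a detected count, however, so it does not reveal the imaging rate.

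**The pause rule is not a between-arm comparison.** Correct. It counts apixaban events only and leads to DSMB evaluation, not automatic termination; enrolled patients continue.

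**It is a small pilot reviewed patient by patient (section 15.2), and further detail may sit in the separate SAP or DSMB charter.** Individual review would help with one or two events, but reviewing positive scans does not show how many patients were never scanned. Section 4.1 still states a non-inferiority hypothesis and section 15.3 a between-arm test. If the SAP or charter already requires an imaging record, the point is met.

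**Other components also depend on work-up**, such as Type 2 bleeding that prompts evaluation. True, and a wider issue of open-label ascertainment; it does not remove this gap.

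**Conclusion.** The gap is real: an imaging-only event counts in the primary composite, in a secondary endpoint and in the pause rule, with no scheduled imaging and no imaging record, in an open-label trial. As written, the trial could not tell a difference in thrombus from a difference in how often patients were imaged.

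Whether such a difference will arise, and which arm it would favor, is unknown. Under the assumed 5% to 10% risk and 80% v 40% imaging, the effect is about 0.4 to 0.8 detected cases per 20, at most 2 to 4 percentage points of the composite and mainly silent thrombus. The pause probability is sensitive to apixaban imaging frequency (at 10% risk, 19% at 40% imaging and 48% at 80%), but not to imaging on warfarin. Every rate here is an assumption. The structural point does not depend on the values; its importance does.

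**What to change.** No imaging, visit or assessor need be added.

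1. On the eCRF, for both arms from randomization to week 24, record the date, modality and reason for each clinically ordered echocardiogram or CT that shows the aortic root. Report the imaging rate by arm.
2. Prespecify a sensitivity analysis of the 24-week composite that leaves out aortic root thrombus not accompanied by another primary-endpoint event, reported beside the unchanged primary analysis. Where another event occurs, use that event's date, so that scan timing plays no part. This rule is objective; labelling a thrombus incidental would be a judgement by staff who know the arm.
3. When the pause rule is reached, give the DSMB the imaging log and the reason for imaging for each aortic root thrombus.

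The SAP is still to be finalized (section 15.1), which is the natural place for item 2.

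Cost: some chart-abstraction time and a second version of the composite, which will be imprecise with few events. The log measures unequal imaging but does not remove it. The sensitivity analysis sets aside genuine silent thrombus, so it should accompany the primary result and not replace it.

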19.3 Appendix C - Schedule of Assessment

Visit number	0	1	2	3	4	5	6	7	Final Visit
Time of Visit	Enrollment & Randomization	2 weeks (±7D)	4 weeks (±7D)	6 weeks (±7D)	8 weeks (±7D)	12 weeks (±14D)	18 weeks (±14D)	24 weeks (±14D)	28 weeks (±7D)
Virtual Visit		х		х	х		х		х
Inclusion/Exclusion criteria	х								
Information & Informed consent	x								
Medical History &									
Concomitant Meds	x	х	X	X	X	Х	X	X	х
Physical examination & Vitals	x		Х			Х		Х	
Laboratory tests*– CBC, CMP, Mg, aPTT, PT/INR**, LDH, Fibrinogen and D-dimer	х		x		\mathbf{X}^{\dagger}	x		x	
Anti-Xa Level (apixaban arm only)			X			X		X	
Biobank sample collection	x		х			Х		Х	
Pregnancy Test***	x								
Dispense study medication****	x		X			X			
Adverse events		X	X	X	X	X	X	X	X

^{*}Labs obtained within 1 week prior to randomization can be used to assess patient eligibility and apixaban dosing.

^{**}Additional INR monitoring may be required in the warfarin patients to achieve the protocol INR goal.

^{***}Pregnancy test only required in females of childbearing potential (age < 50 years).

^{****}Randomization will occur at enrollment. Study drug treatment will be initiated as described in protocol above.

[†]Week 8 visit is conducted virtually, remote labs to be collected include: CBC (white blood cells, hemoglobin, platelet count), CMP (sodium, potassium, BUN, creatinine, magnesium, AST/ALT, total and direct bilirubin, albumin, total protein, alkaline phosphatase), prothrombin time/INR, LDH.

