7.3 Study Intervention Phase

Study treatment will be using the target dose of apixaban 5mg po BID or warfarin po daily for a goal INR of 2.0 to 2.5. All patients will be treated with aspirin 81mg daily as per the IFU. Randomized participants will receive the first dose of study drug as follows:

- LVAD patients randomized to warfarin will begin treatment once all anticipated surgical procedures are complete and the patient is deemed stable for transfer out of the ICU. Warfarin will be overlapped with low intensity heparin until the INR is at least 2.0. Warfarin will be dosed to maintain an INR goal of 2.0-2.5. For ambulatory LVAD patients, warfarin therapy will be continued.
- LVAD patients randomized to apixaban will transition from heparin to apixaban once all anticipated surgical procedures are complete and the patient is deemed stable for transfer out of the ICU. Heparin will be discontinued at the same time apixaban is initiated. For ambulatory LVAD patients on warfarin, warfarin will be transitioned to apixaban when the INR < 2.0.

Dose adjustments of apixaban will not occur. Dose adjustments of warfarin will be made no less than every 4 weeks to achieve the goal INR of 2.0 to 2.5. Participants will return to clinic according to the schedule shown in Appendix C.

For patients upgraded on the transplant list from a status 4 or below to a status 1-3, apixaban will be transitioned to warfarin, to allow for drug reversal at time of transplant. Patients randomized to the apixaban arm will be replaced to ensure 20 LVAD patients are exposed to apixaban over the duration of the study. Warfarin patients will not be replaced, as warfarin is standard of care therapy for LVAD patients.

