9.7 Randomization, Stratification and Blinding

Patients will be consented, enrolled, and randomized at the first study visit. Participants will be randomized using procedures determined by the CC to one of 2 treatment groups. Participants will be randomized in a 1:1 allocation ratio using a permuted block design with stratification based on time from LVAD implant (<3 months v. \geq 3 months). Enrollment of existing HM3 LVAD patients, implanted \geq 3 months will be capped at 20 to ensure adequate representation of newer LVAD implants who have a higher risk of thromboembolic adverse events.

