14.2 Definitions

14.1.1 Adverse Events

An adverse event (AE) is any untoward medical occurrence associated with the use of a drug in a participant, whether or not it is considered directly related to the drug or biologic related. An AE can therefore be any undesirable sign, symptom or medical condition occurring after starting study drug, even if the event is not considered to be related to the pharmaceutical product. Study drug includes the drug under evaluation, and any reference drug given during any phase of the trial. Safety monitoring for adverse events will begin upon randomization.

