19.2 Appendix B - Adverse Event Definitions

- Arrhythmias: Any documented arrhythmia that results in clinical compromise, or requires hospitalization or treatment. Arrhythmias will be further classified as sustained ventricular arrhythmia or sustained supraventricular arrhythmia
- Arterial non-CNS thromboembolism: Acute systemic arterial perfusion deficit in any non-cerebrovascular organ system due to thromboembolism confirmed by 1 or more of the following: 1) standard clinical and laboratory testing, 2) operative findings, 3) autopsy findings
- Bleeding: the location/source of the bleed will be recorded and subsequently categorized as follows; CNS bleeding will be captured under cerebrovascular event/stroke
 - Type 2: Any overt, actionable sign of hemorrhage that does not fit the criteria for Type 3, 4, or 5 but does meet at least one of the following criteria:
 - 1) requiring non-surgical, medical intervention by a healthcare professional
 - 2) leading to hospitalization or increased level of care; or
 - 3) prompting evaluation
 - Type 3a
 - Overt bleeding accompanied by hemoglobin drop of 3 to < 5 g/dL
 - Any transfusion with overt bleeding
 - o Type 3b
 - Overt bleeding plus hemoglobin drop 5 g/dL or greater
 - Cardiac tamponade
 - Bleeding requiring surgical intervention for control (excluding dental/nasal/skin/hemorrhoid)
 - Bleeding requiring intravenous vasoactive agents
 - Type 4: VAD implantation-related bleeding (includes concomitant cardiac or non-cardiac surgical procedure)
 - Reoperation after the closure of incision or incisions used to implant the VAD to control bleeding
 - ≥ 50 kg: ≥ 4U pRBC within any 48 hours during the first 7 days postimplant
 - < 50 kg: ≥ 20 cm³/kg pRBC within any 24 hours during the first 7 days post-implant
 - Chest tube output > 2 liters within 24 hours
 - Type 5a: Probably fatal bleeding; no autopsy or imaging confirmation but clinically suspicious
 - Type 5b: Definite fatal bleeding; overt bleeding or autopsy or imaging confirmation
 - o For all types of bleeding, the event will be classified as:
 - Patient-related (e.g., coagulopathy unrelated to surgical technique such as non-adherence with anticoagulation medication resulting in inappropriately high level of anticoagulation, hepatic failure)
 - Management-related (e.g., related to surgical technique, hypertension, bleeding in the setting of inappropriate levels of anticoagulation)

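### Newly implanted inpatients are randomised before they can start study drug, so pre-dose bleeds count in the primary composite and, before any apixaban is given, toward the apixaban pause rule

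*Combined protocol and SAP*

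**What the plan says.** **Randomisation.** Section 9.7: "Patients will be consented, enrolled, and randomized at the first study visit". Section 11.1 places that visit after the LVAD implant. The Appendix C footnote separates the two dates: "Randomization will occur at enrollment. Study drug treatment will be initiated as described in protocol above".

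**Drug start.** Under 7.3, inpatients in the apixaban arm "will transition from heparin to apixaban once all anticipated surgical procedures are complete and the patient is deemed stable for transfer out of the ICU". The warfarin arm has the same condition: "LVAD patients randomized to warfarin will begin treatment once all anticipated surgical procedures are complete", again with readiness to leave the ICU. Ambulatory patients assigned to apixaban wait until the INR is below 2.0 (7.3, 11.1).

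**Event window.** Section 14.1.1: "Safety monitoring for adverse events will begin upon randomization". The same section also describes an adverse event as arising after study drug is started. Section 14.1.8 captures serious events from signed consent. Section 15.1 attributes endpoints to the randomised arm in all randomised participants. The primary endpoint (12.1) lists bleeding with no limit by type and no first-dose condition.

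**Bleeding types and pause rule.** Appendix B defines Type 4 as bleeding related to the VAD implantation and defines major bleeding as Types 3-5. Section 17.2 pauses enrolment for DSMB evaluation at four or more major bleeds in the apixaban arm. It sets no condition that apixaban has been started.

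**The concern.** A patient randomised to apixaban who bleeds while still on heparin is an event for apixaban under two rules. In the primary composite both arms share the gap, so the effect is noise common to both. That noise pulls the comparison toward no difference, and since the hypothesis in 4.1 is non-inferiority, this pull is not conservative. The pause rule is more exposed. It looks at the apixaban arm alone, with no comparator to absorb bleeds due to surgery or heparin, and its threshold is only four events. Enrolment could be paused over bleeds that apixaban could not have caused.

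**Working it through.** There is no figure in the plan to reproduce: 15.2 says the 40 patients were not statistically derived, and no event rates are given. The check has two parts: what the rules count, and an illustration under assumed rates.

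**1. What the rules count.** Section 7.3 provides for randomised patients with surgery still outstanding, so a gap between randomisation and first dose is possible. By 14.1.1 and 15.1, events in the gap belong to the randomised arm. Neither 12.1 nor 17.2 removes them. The 72-hour treatment-emergent rule in 14.1.8 sets only an end to the window and is not linked to the endpoint or the pause rule.

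**2. Pause rule.** Inputs:
- threshold of 4 (17.2);
- 20 apixaban patients (half of 40; 7.3);
- on-drug major-bleed risk over 24 weeks p = 10% (assumed; 5% and 15% also shown);
- m patients who also carry a pre-dose major-bleed risk q (assumed).

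The cap of 20 patients at 3 months or more leaves at least about 20 earlier ones if 40 are enrolled, so about 10 per arm. Not all of those 10 need be ICU inpatients, so m = 5 is shown too. Each patient counts once.

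Risk for a patient with a gap: 1 - (1 - p)(1 - q). With p = 10%, this is 14.5% at q = 5% and 19.0% at q = 10%. The chance of at least 4 is the upper tail of the sum Bin(m, 1 - (1 - p)(1 - q)) + Bin(20 - m, p).

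| On-drug risk p | Post-dose bleeds only | m = 5, q = 5% / 10% | m = 10, q = 5% / 10% |
|---|---|---|---|
| 5% | 1.6% | 3.1% / 5.3% | 5.5% / 12.1% |
| 10% | 13.3% | 17.6% / 22.2% | 22.3% / 32.8% |
| 15% | 35.2% | 40.4% / 45.6% | 45.6% / 55.6% |

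Pre-dose bleeds alone would rarely trip the rule. P(at least 4 of 10) is 0.1%, 1.3% and 5.0% at q = 5%, 10% and 15%. The effect comes from adding them to on-drug bleeds.

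**3. Primary composite.** Assumed post-dose risks are 20% (warfarin) and 36% (apixaban), a relative risk of 1.80 and a hazard ratio of 2.0, since 1 - 0.80² = 0.36. Pre-dose risk is q in both arms, early stratum only; the strata are equal.
- q = 5%: early-stratum risks are 1 - 0.95 × 0.80 = 0.240 and 1 - 0.95 × 0.64 = 0.392. Averaged with the late stratum: 0.220 and 0.376, relative risk 1.71.
- q = 10%: 0.280 and 0.424; averaged 0.240 and 0.392, relative risk 1.63.
- q = 15%: 0.320 and 0.456; averaged 0.260 and 0.408, relative risk 1.57.

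This gives every early-stratum patient a gap, so within equal strata it is the larger end of the effect. For scale, 20% and 36% of 20 is about 4 and 7 events. The 95% interval for the hazard ratio is then roughly a factor of exp(1.96 × √(1/4 + 1/7)) = 3.4 either way.

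**The case against.** The case on the other side is substantial:

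- **The gap may be short.** Visit 0 follows the implant, and 8.2 and 8.3 require written consent, no ongoing inotropes, no active bleeding, haemoglobin of at least 8.0 g/dl and platelets of at least 100,000. Many implant bleeds will precede randomisation. Section 11.1 does not repeat the ICU condition, and Appendix C marks dispensing at Visit 0. This stands as a limit on size. It does not remove the gap that 7.3 allows.
- **Type 4 is not confined to the gap.** A reader might infer that every Type 4 bleed precedes the first dose and so cannot be due to study drug. Appendix B does not support that: the 7-day limit applies only to the two transfusion criteria. Reoperation for bleeding and chest tube output above 2 litres carry no such limit and can follow the first dose.
- **Not every patient under 3 months is in the ICU.** Section 8.1 admits ambulatory patients. The number with a gap is unknown.
- **Counting from randomisation is ordinary intention to treat**, and both arms share the gap. This is right for the primary endpoint, where the shift is small beside the sampling error. No margin is stated, and 15.2 disclaims statistical significance, so a biased non-inferiority verdict would be too strong a reading.
- **The pause has safeguards.** It halts enrolment only, the DSMB reviews the cases, Appendix B classifies the cause of each bleed, and the DSMB charter, which is not in the documents, may settle attribution. These soften the consequence, but the trigger as written in 17.2 still counts the event.

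A reader might also infer that open allocation influences when a patient is judged stable. Both arms share one criterion, and nothing in the documents shows such an influence.

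**Conclusion.** The point holds in a limited form. As written, pre-dose bleeds in newly implanted inpatients count in the composite for both arms and in the apixaban pause total before apixaban has been given. The consequence for the pause rule is the more important: under the assumed 10% on-drug risk, the chance of a pause rises from 13% to 22-33% with 10 affected patients, or to 18-22% with 5. Dilution of the primary comparison is modest, from a relative risk of 1.80 to about 1.71-1.57 under the assumptions shown. All rates, the number of patients affected and the length of the gap are assumptions. What the documents establish is the counting rule. Because the correction is cheap, it is worth making before enrolment.

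**What to change.** 1. Keep consent at enrolment. Amend 9.7 and Appendix C so that inpatients are randomised when the existing start condition in 7.3 is met, with eligibility confirmed then. Date the 24 weeks from randomisation. The intention-to-treat analysis is unchanged.
2. In 17.2, count toward the apixaban bleeding total only major bleeds on or after the first apixaban dose. Report any bleed between randomisation and first dose separately to the DSMB. This also covers ambulatory patients waiting for the INR to fall below 2.0, whom the first change does not reach. Align the DSMB charter.
3. Reconcile the event-start statements in 14.1.1 (after study drug is started; at randomisation) and 14.1.8 (at signed consent), and state one start date for endpoint events.
4. If the time of randomisation cannot move, keep the intention-to-treat primary analysis and add a sensitivity analysis that counts events from first dose.

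Cost: no added visits. A few consented patients may never reach randomisation, which matters somewhat in a single-centre study of 40. Some eligibility laboratory tests may need repeating when they fall outside the 1-week window in 11.1.
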